7.1 Study Subjects

7.1.1 Disposition of Subjects

A subject is enrolled in the study when he/she signs and dates the Patient Informed Consent. The study is expected to be conducted at approximately 50 sites worldwide in the regions listed in Section 5. Each region is expected to enroll approximately 200 subjects, with a total of approximately 1,200 subjects. A flow chart similar to figure 2 will be created to describe patient disposition.

Figure 2: patient disposition flow chart

Study exits will be summarized according to exit reason. Violation of inclusion and exclusion criteria at baseline will be summarized for all enrolled patients.

7.1.2 Clinical Investigation Plan (CIP) Deviations

Deviations from the clinical investigation plan will be collected as deviations on the Study Deviation eCRF. Deviations will be summarized in the final report in a table by coded category. Deviation coding will be performed by Medtronic, and the coding will be collected on the MDT Deviation eCRF. The

number of deviations per category, the number and percentage of subjects with a deviation in this category will be reported.

7.1.3 Analysis Sets

Study manager, data manager and statistician will determine the visit cut-off date and received data cut-off date for the final data base lock as suitable.

Data from all patients who signed the informed consent document, are enrolled and have no inclusion or exclusion criteria violation will be analyzed. This set of patients will be referred to as the Enrolled Population. Depending on the analysis objective, statistical analyses based on subsets of the Enrolled Population will also be produced, as defined in the “Determination of Patients/Data for Analysis” of each of the analysis objectives described in Section 7.9.

7.2 General Methodology

Data summaries for categorical data will include count, e.g., number of patients, and/or number of events, and a percentage relative to the total number of patients/events. The denominator will be explicitly identified when not clear from the context. Continuous variables will be represented by mean and standard deviation, except when the distribution of the variable is highly skewed in which case median and quartiles will be reported.

P-values for hypothesis testing will be evaluated based on two-sided testing using significance level of 0.05. Confidence intervals will be reported as two-sided 95% confidence intervals.

7.3 Center Pooling

The study is expected to be conducted at approximately 50 sites worldwide, within 6 regions (see details of regions in Section 5). Data will be pooled across centers within the same region and analyses will be presented by region. Within each region, heterogeneity in the primary endpoint across centers will be evaluated using the Fisher Exact test. If this test is significant at the 0.05 level, further investigation of the data may occur to determine the source of the heterogeneity.

7.4 Handling of Missing, Unused, and Spurious Data and Dropouts

Because this is a feasibility study and no hypothesis testing is involved in any of the study objectives, the main analysis for each objective will not account for missing data. All available data will be used for analyses. In the unlikely presence of any unused or spurious data, such data will be listed or summarized in a dedicated table and the reasons for not using it will be explained. Drop outs between each study visit will also be summarized by region and overall.

7.5 Adjustments for Multiple Comparisons

No adjustment for multiple comparisons is planned due to the exploratory nature of the study.

7.6 Demographic and Other Baseline Characteristics

Standard baseline and relevant medical history will be collected on the e-CRFs for all enrolled subjects. Baseline and medical history variables to be summarized include, but are not limited to: age, sex, region of enrollment, cardiovascular history, arrhythmia history, and cardiovascular medications.

For continuous variables, mean, standard deviation, median, and range will be reported. For categorical variables, frequency and percentage will be reported. Baseline information will be summarized overall and by region for all enrolled subjects.

7.7 Treatment Characteristics

Subjects are treated per standard of care, there are no treatment requirements and there is no investigational device. Any treatment information that will be collected will be summarized, including devices and medications.

7.8 Interim Analyses

No interim analysis is planned for this study. A sample size re-estimation may be performed instead, as described in Section 6.2.

7.9 Evaluation of Objectives

7.9.1 Primary Objective

Characterize the proportion of post-acute MI patients who are referred for sudden cardiac death risk (SCD) stratification and management.

7.9.1.1 Hypothesis

This is a characterization study, and so there are no hypotheses for this objective.

7.9.1.2 Endpoint definitions

The endpoint will be defined as the clinician's determination to refer the subject for SCD risk stratification and management. The pre-defined reasons for this referral are:

- Subject's LVEF at 3 months determined to be up to 40%

- Subject experiences unexplained syncope, ventricular arrhythmia, AV block, clinically significant palpitations, new onset bundle branch block, conduction abnormalities, or symptomatic bradycardia.

7.9.1.3 Analysis Methods

Subjects will be evaluated during their three months visit (chronic phase, $\geq 40-90$ days after MI) for determination of the need for SCD risk stratification and management. As of this visit, subjects will be partitioned into several groups: died of cardiovascular causes prior to reaching the 3 months visit, exited or died of non-cardiovascular or unknown causes prior to reaching 3 months visit, reached the 3 months visit and exited because of $\text{LVEF} \geq 50\%$, reached the 3 months visit and had at least one reason for referral for SCD risk stratification and management, reached the 3 months visit and had no reason for referral for SCD risk stratification and management.

Subjects classified as “died of cardiovascular causes” will be all subjects with subject status “death” within the exit CRF and with primary cause of death “non-sudden cardiac death” or “sudden cardiac death” within the death CRF.

Subjects classified as “exited or died of non-cardiovascular or unknown causes” will be all subjects with subject status “death” within the exit CRF and with primary cause of death “non-cardiovascular death” or “unknown classification” within the death CRF and all subjects with subject status “adverse event, lost to follow-up, physician decision, sponsor request or withdrawal by subject” in the exit CRF.

Subjects classified as “reached the 3 months visit and exited because of $\text{LVEF} > 50\%$ ” will be all subjects that will have completed the three months visit and will have subject status “other” within the exit CRF and will have a result of LVEF measurement higher or equal than 50% within the LVEF CRF.

Subjects classified as “reached the 3 months visit and had at least one reason for referral” will be all subjects that will have completed the three months visit and that in the referral CRF will have answer “yes” to the question “does the subject meet referral criteria” and will have at least one reason for referral selected underneath the question “if yes, indicate referral criteria met”.

Subjects classified as “reached the 3 months visit and had no reason for referral” will be all subjects that will have completed the three months visit and that will have answer “no” to the question “does the subject meet referral criteria” in the referral CRF.

Descriptive statistics will be used to summarize these groups and displayed as shown in the example Table 2 below.

Table 2: Number (%) of subject in each group between enrollment and the 3 months visit

		Enrolled Population
Region 1	Died of cardiovascular causes	XX/XX (XX.XX%)
	Exited or died of non-cardiovascular or unknown causes	XX/XX (XX.XX%)
	Reached the 3 months visit and exited because of LVEF \geq 50%	XX/XX (XX.XX%)
	Reached the 3 months visit and had reasons for referral	XX/XX (XX.XX%)
	Reached the 3 months visit and had no reasons for referral	XX/XX (XX.XX%)
Region 2	Died of cardiovascular causes	XX/XX (XX.XX%)
	Exited or died of non-cardiovascular or unknown causes	XX/XX (XX.XX%)
	Reached the 3 months visit and exited because of LVEF \geq 50%	XX/XX (XX.XX%)
	Reached the 3 months visit and had reasons for referral	XX/XX (XX.XX%)
	Reached the 3 months visit and had no reasons for referral	XX/XX (XX.XX%)
...
Overall	Died of cardiovascular causes	XX/XX (XX.XX%)
	Exited or died of non-cardiovascular or unknown causes	XX/XX (XX.XX%)
	Reached the 3 months visit and exited because of LVEF \geq 50%	XX/XX (XX.XX%)
	Reached the 3 months visit and had reasons for referral	XX/XX (XX.XX%)
	Reached the 3 months visit and had no reasons for referral	XX/XX (XX.XX%)

The same summary statistics will be computed at the 6 months and at the 12 months visits and displayed in tables similar to Table 1, except for the group “exited because of LVEF \geq 50%” as patients are exited from the study for this reason at the 3 months visit only.

Note that at the three months visit, subjects with a LVEF \geq 50% will be exited from the study regardless of other reasons for referral. The proportion of those subjects that had a reason for referral other than LVEF will be computed by region and overall.

Among the subjects with a reason for referral during their three months visit, the proportions and Wilson score 95% CI of those who were referred for sudden cardiac death risk (SCD) stratification and management will be computed.

The subjects with a reason for referral (denominator) will be all subjects that at the three months visit will have at least one referral criterion met in the referral CRF. The subjects referred (numerator) will be

all subjects that will have completed the three months visit and that will have answer “yes” to the question “has the subject been referred or invited for SCD risk stratification” in the referral CRF.

An example SAS code for the computation of the proportions for each region is provided below:

```
proc freq data = referral;
  by region;
  table referred/binomial (cl = wilson) alpha = 0.05 out = perc;
  ods output binomialCLs=percConf;
run;
```

The results will be shown for each region and overall in a table similar to the example table below:

Table 3: percentage (95% CI) of subjects referred for sudden cardiac death risk (SCD) stratification and management, among the subjects with at least one reason for referral at the 3 months visit (chronic phase)

Region	Proportion Referred	95% CI
Region 1	XX/XX (XX.XX%)	(XX.XX% - XX.XX%)
Region 2	XX/XX (XX.XX%)	(XX.XX% - XX.XX%)
...
Overall	XX/XX (XX.XX%)	(XX.XX% - XX.XX%)

A subject not referred for SCD risk stratification and management during their three months visit may later be referred. Thus, similar descriptive statistics may be generated at the 6 and at the 12 months post-baseline visits and displayed in a table similar to table 2 above.

Further, as part of an attempt to continually train the physicians on referring subjects with a reason for referral, periodic feedbacks on referral rates will be provided. Whether these periodic feedbacks will have an impact on referral rate will be investigated by producing, for each region and overall and over time, a penalized B spline plot. A SAS code similar to the below will be used:

```
ods graphics on / attrpriority=none;
proc sgplot data=referral noautolegend;
  title 'Penalized B-Spline for each region';
  styleatrrs datalinepatterns=(solid);
  pbspline y=prop x=time/group=region;
run;
```

Additional analyses may be provided and described in the final report.

Additionally to the analyses described above, logistic regression models might be used overall and by region, to estimate the odds ratios of referring patients for SCD stratification and management

depending on different factors, such as age, gender, LVEF≤40% versus any other reason for referral, physician's specialty, PCI versus non-PCI patients, STEMI versus non-STEMI patients. An example SAS code similar to the below will be used:

```
proc logistic data = referral;
  by region;
  class factor/descending;
  model referred (event = '1') = factor/expb;
  oddsratio factor;
  ods output ParameterEstimates = ParEstim;
  ods output OddsRatiosWald = OREstim;
run;
```

where referred is the outcome and is equal to 1 if the subject has been referred and 0 otherwise, factor is the independent factor of interest (eg: reason for referral, physician's specialty). Results of the logistic regression model will be displayed by means of either tables or plots.

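### The five Table 2 groups in SAP 7.9.1.3 are called a partition, but their CRF rules overlap and leave out subjects who miss the 3-month visit and stay in the study

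*SAP*

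**What the plan says.** SAP 7.9.1.3 states that "subjects will be partitioned into several groups" as of the 3-month visit. It names five groups: cardiovascular death before the visit; exit, or death from non-cardiovascular or unknown causes, before the visit; visit reached and exited for LVEF of 50% or more; visit reached with a reason for referral; visit reached without one. Table 2 reports each as a percentage of the Enrolled Population, by region and overall.

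Each group then gets a CRF rule:

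- The LVEF-exit group consists of subjects who "will have completed the three months visit and will have subject status" other on the exit form and who "will have a result of LVEF measurement higher or equal than 50% within the LVEF CRF".
- The reason group needs a completed visit and a referral form answered yes, and its members "will have at least one reason for referral selected underneath the question" about which criteria were met.
- The no-reason group "will be all subjects that will have completed the three months visit and that will have answer" no to the referral-criteria question.
- The two death and exit groups are identified only from the exit and death forms, by status and cause.

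The same section notes that subjects with LVEF of 50% or more "will be exited from the study regardless of other reasons for referral", and adds: "The proportion of those subjects that had a reason for referral other than LVEF will be computed by region and overall". The Table 3 denominator is set separately as "all subjects that at the three months visit will have at least one referral criterion met in the referral CRF".

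Referral status is a required item at follow-up visits (Protocol 9.3 Table 2 and 9.6.1). Protocol 9.6 foresees that a visit may be missed. SAP 5.1 has a rule for late visits but none for missed ones.

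**The concern.** Table 2 is the pathway flow table for the primary objective. A reader will take its rows as shares of the enrolled population that add to 100%. Under the written rules they need not. Recovered subjects can be counted in their own row and again among those with or without a reason, and some subjects can appear in no row. Recovery, later death and missed visits may differ by region, so the distortion may differ too, and the table is meant to be read region by region. Two programmers could also produce different tables from the same data, one applying the rules literally and one imposing an order that the SAP does not state.

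The gap for missed visits also reaches SAP 6.2. That section uses observed deaths and drop-outs, and the proportion with a reason among completed visits, to decide how many subjects a region must enrol.

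**Working it through.** **1. The plan's own figure (SAP 6.1).** Inputs: proportion referred 0.70, half-width 0.125, 95% Wilson interval, 30% with a reason, 10% attrition. For x referred out of n, with p = x/n and z = 1.96, the Wilson half-width is z·√(p(1−p)/n + z²/(4n²)) / (1 + z²/n). The exact binomial probability that it is at most 0.125 is 0.784 at n = 53 and 0.897 at n = 54, so 54 is the first n to reach 0.80. Then 54/0.30 = 180 and 180/0.90 = 200. The plan's 54, 180 and 200 reproduce.

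**2. The rules side by side (SAP 7.9.1.3).**

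| Row | Visit completed? | Further condition | Excludes other rows? |
|---|---|---|---|
| CV death | not asked | exit and death forms | no time limit |
| Other exit or death | not asked | exit and death forms | no time limit |
| LVEF exit | yes | exit status other, LVEF of 50% or more | referral answer not asked |
| Reason | yes | referral form yes, with a criterion | LVEF exits not excluded |
| No reason | yes | referral form no | LVEF exits not excluded |

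Three consequences follow:

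- An LVEF exit with a completed referral form meets row 3 and also row 4 or row 5.
- A subject who completes the 3-month visit and later dies, or exits with a listed status, meets row 1 or 2 and also row 4 or 5. The labels of rows 1 and 2 say the event precedes the visit, but their CRF rules do not. The SAP supports the final report, when later exit and death forms will be in the database.
- A subject who misses the visit and stays in the study meets no row.

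**3. Size of the LVEF overlap.** Take a region of 200 enrolled with 20 deaths or drop-outs before the visit and 180 completers. Let f be the share of completers exited for LVEF of 50% or more. The documents give no value, so f is an assumption. Suppose every exit has a referral answer, no visit is missed and nobody dies or drops out later. The rows then sum to 20 + 180f + 180 = 200 + 180f.

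- f = 10%: 218/200 = 109%
- f = 25%: 245/200 = 122.5%
- f = 40%: 272/200 = 136%

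Each later death or listed exit among the other completers adds one more to the total.

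**4. Overlap and gap together.** Let m be the share of enrolled subjects who miss the visit but stay in the study (also an assumption).

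- m = 5%, f = 30%: 10 subjects are in no row, completers are 170, and the rows sum to 20 + 51 + 170 = 241, or 120.5%, while covering 190 distinct subjects.
- m = 10%, f = 10%: the rows sum to 20 + 16 + 160 = 196, or 98%. This looks nearly right although 20 subjects are missing and 16 are counted twice.

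**5. Effect on SAP 6.2.** With m = 5%, the observed exit rate is 20/200 = 0.10 and the proportion with a reason is 51/170 = 0.30. The formula returns (54/0.30)/0.90 = 200, so it calls for no change. Yet 170 × 0.30 = 51 subjects have a reason.

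| Missed (assumed) | With a reason | Probability of target width | Enrolment needed, 180/(0.90 − m) |
|---|---|---|---|
| 2% | 52.8 (taken as 52) | 0.72 | 204.5, so 205 |
| 5% | 51 | 0.65 | 211.8, so 212 |
| 10% | 48 | 0.52 | 225 |

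**The case against.** The strongest reply is that exclusive groups are plainly intended. The SAP says so, gives LVEF exits their own row, and labels the first two groups as events before the visit. The overlap with the reason row was foreseen: the SAP will report how many LVEF exits had another reason. With E exits and a share s of them with another reason, a reader could subtract sE from the reason row and (1 − s)E from the no-reason row. Missed visits should also show up elsewhere, since missing data are to be reported as counts and percentages (SAP 9) and deviations by category (SAP 7.1.2). Drop-out is not defined in 6.2 so as to exclude them.

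Part of this stands. The information on LVEF exits is largely recoverable, and a no-reason entry is true of a recovered subject who meets no criterion. But the subtraction works only if every exit has a referral answer, it does nothing for later deaths and exits, and it asks the reader to repair a published table. An undefined drop-out term does not settle how 6.2 treats a missed visit.

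Four stronger readings are tempting, and the documents do not support them:

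- *The primary proportion is distorted or undefined.* It is not. Table 3 counts all subjects with a criterion met at the 3-month visit, without an LVEF exclusion, so LVEF exits with another reason are in its denominator.
- *Every LVEF exit is counted twice.* This holds only where the referral form is answered no, or yes with a criterion. The required item makes an answer likely, but the forms are under separate cover (Protocol Appendix A) and their skip logic cannot be checked.
- *Everyone who misses the visit is in no row.* One who later dies or exits with a listed status is caught by row 1 or 2, because those rules have no time limit. A late visit is not a missed one.
- *The planned 54, 180 and 200 are wrong.* They reproduce, and the Table 2 overlap does not touch them.

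**Conclusion.** The point holds for Table 2 and for the re-assessment formula. As written, the CRF rules do not produce the partition that SAP 7.9.1.3 announces. There are two sources of double counting (LVEF exits with a completed referral form, and deaths or exits after a completed visit) and one gap (visit missed, still in study).

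The sizes are illustrations and not forecasts. The 109% to 136% range rests on an assumed 10% to 40% recovery share among 180 completers. The fall in the probability of the target width from 0.897 to 0.65 rests on an assumed 5% of missed visits without exit, with the plan's 30% and 70% taken as true. No hypothesis is tested and the primary proportion keeps its own denominator. This should be corrected before the analysis, but it does not threaten the primary result.

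**What to change.** 1. Limit the two death and exit rows in SAP 7.9.1.3 to events before the 3-month visit, in the CRF rules as well as in the labels. Without that limit, any ordering that starts with deaths would take subjects who die after a completed visit out of their correct row.
2. Restrict the reason and no-reason rows to completers not exited for LVEF of 50% or more, and split the LVEF-exit row by other criterion yes or no. Note that those with yes stay in the Table 3 denominator, so that denominator is the reason row plus this sub-row, subject to the late-visit rule in item 3. Use one threshold sign throughout, since the group's label in its definition reads above 50% while the rule reads 50% or more.
3. Add a row for subjects in the study whose 3-month visit was not done, and say which Table 2 row a late visit takes. SAP 5.1 moves a late referral to the 6-month visit but keeps a late non-referral at 3 months.
4. In SAP 6.2, count subjects whose 3-month window has closed without a visit in the attrition rate, treating late visits as decided in item 3.

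Check with f = 30% and m = 5%: 20 deaths or exits, 10 visits not done, 51 LVEF exits and 119 other completers sum to 200, or 100%.

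The Table 3 rule needs no change, and the primary proportion need not be shown in two versions. The cost is SAP wording, one new row and one split row. No new data are collected.

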5.1. Study Design

This study is a prospective, non-randomized, single-arm, multi-site, global, post-market study. There is no investigational device and there is no control group; subjects can be implanted, if indicated and referred, with any brand or model of a market released ICD/CRT-D.

The study is expected to be conducted at approximately 50 sites worldwide. Participating regions are: China, India, Korea, Middle East, Africa, Central Asia, & Turkey (MEACAT) (including Egypt, Pakistan, Saudi Arabia, South Africa and Tunisia), South East Asia (SEA) (including Brunei, Indonesia, Malaysia, Philippines, Singapore and Thailand) and Taiwan. Additional countries could participate within these regions. Each region is expected to enroll approximately 200 subjects. The study is expected to enroll approximately 1,200 subjects.

Prior to study site initiation, current referral information will be collected from sites, and investigators and other site clinical personnel will be trained using educational materials (available under a separate cover) that address the importance of EF measurement and care pathway for post-MI patients. Apart from the educational material, there is no intervention and there are no requirements for treatment of

the patients. Referral of patients to SCD risk stratification and management is at the discretion of the physicians.

[figure not shown]
Methods incorporated in the study design to minimize potential bias include (but are not limited to):

- Subject demographics will be collected at baseline for potentially analyzing differences that may affect the endpoints.
- All study clinicians and Medtronic personnel will be trained on the corresponding aspects of the study using standardized training materials.
- All study clinicians and Medtronic personnel will be trained on and required to follow the Protocol.
- Sites will be encouraged to approach any eligible patients meeting inclusion/exclusion criteria
- Each region is expected to enroll approximately 200 subjects to have at least 80% power to achieve a sufficient number of patients referred for SCD risk stratification and management.
- For each region, sites where the same physician acts both as an interventional cardiologist and as an electrophysiologist will be limited to a maximum of 20% of all sites.

No interim analysis is planned, but a sample size re-assessment for each region may be produced, as described in Section 6.2.

See Figure 1 for further detail on study procedures.

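### The primary denominator in SAP 7.9.1.3 comes only from the site's referral CRF answers, so a recorded 3-month LVEF of 40% or less does not by itself bring a subject in

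*SAP*

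**What the plan says.** SAP 7.9.1.2 defines the endpoint as the clinician's decision to refer and names the reasons for it. The first is "LVEF at 3 months determined to be up to 40" per cent; the others are symptoms, arrhythmias and conduction findings.

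SAP 7.9.1.3 turns this into data rules:

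- The group with a reason for referral is made up of subjects answered *yes* to "does the subject meet referral criteria" who also "will have at least one reason for referral selected underneath the question" on the criteria met. A *no* places the subject in the group without a reason.
- The denominator of the primary proportion is every subject who at the 3-month visit "will have at least one referral criterion met in the referral CRF".
- The numerator uses another item on the same form: "has the subject been referred or invited for SCD risk stratification".
- The LVEF CRF enters this partition only for the early-exit group, whose members "will have a result of LVEF measurement higher or equal than 50% within the LVEF CRF".

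No step derives an LVEF of 40% or less from the LVEF CRF, and none says which form prevails when the two disagree. By contrast, the denominator of the refusal objective (SAP 7.9.5.2) is worded on measured LVEF of 40% or less, or ECG or clinical findings.

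The term referral criteria is not used uniformly. Protocol 9.6 speaks of subjects with LVEF of 40% or less *or* meeting one of the referral criteria, and then lists the latter without LVEF. The Figure 1 footnotes (Protocol Section 6, SAP 5.1) also list referral criteria without LVEF.

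**The concern.** The study measures how often patients with a reason for referral are referred. Who has a reason should therefore be fixed, as far as possible, independently of whether referral took place. For LVEF this can be done, because the value is recorded on its own form. The SAP instead relies on a second, interpreted answer given by the same site on the form that records the referral.

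A wrong *no* can arise in good faith. A site that follows Protocol 9.6 or the Figure 1 footnote could read referral criteria as the symptom and rhythm list, and answer *no* for a subject whose only reason is a low LVEF. Such a subject leaves the primary proportion unnoticed. If that happens more often when no referral was made, the reported proportion is too high, and more enrolment does not correct it. The SAP would also hold two populations with a reason for referral, one from the referral CRF (primary) and one worded on measured LVEF (refusal objective), and the two results need not agree.

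**Working it through.** **1. The plan's own figure.** SAP 6.1 inputs: Wilson 95% interval, half-width 0.125, proportion 0.70, probability at least 80%, 30% with a reason, 10% lost by 3 months. Summing exact binomial probabilities that the Wilson half-width is at most 0.125 gives 78.4% at n = 53 and 89.7% at n = 54. So 54 is the first adequate size; 54/0.30 = 180 and 180/0.90 = 200, as stated. The fix leaves these figures unchanged.

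**2. What the rule does** to a subject whose only reason is a recorded 3-month LVEF of 40% or less:

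| Referral CRF entry | Referred | Place in the primary proportion |
|---|---|---|
| *yes*, criterion ticked | yes | numerator and denominator |
| *yes*, criterion ticked | no | denominator only |
| *no*, nothing ticked | no | absent |
| *no*, nothing ticked | yes | absent |

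The third row pushes the proportion up and the fourth pushes it down.

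**3. Size.** Let p be the true referral proportion among eligible subjects, f the share of non-referred eligible subjects recorded *no*, and g the same share among referred subjects. Then

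observed = p(1 − g) / [p(1 − g) + (1 − p)(1 − f)].

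The documents give neither f nor g; both are assumptions.

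*Errors only among the non-referred (g = 0), 54 eligible:*

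| True p | f = 10% | f = 20% | f = 40% | f = 50% |
|---|---|---|---|---|
| 70% (SAP planning value) | 72.2% | 74.5% | 79.5% | 82.4% |
| 50% | 52.6% | 55.6% | 62.5% | 66.7% |
| 30% | 32.3% | 34.9% | 41.7% | 46.2% |

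Example: p = 0.70 and f = 0.20 gives 37.8/(37.8 + 16.2 × 0.8) = 37.8/50.76 = 74.5%. At p = 0.70 the shifts for f = 20% and 40% are 4.5 and 9.5 points. The Wilson interval for 70% of 54 is 56.8% to 80.6%, a half-width of 11.9 points.

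*Equal errors (f = g):* the factor cancels and observed = p.

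*Errors only among the referred (f = 0, g = 20%), p = 0.70:* 30.24/(30.24 + 16.2) = 65.1%, a downward shift.

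**4. What can be corrected.** The table applies f to all 54 subjects. Symptom and ECG reasons cannot be rebuilt from LVEF, and a subject with low LVEF plus another ticked criterion is already counted. At a given f with g = 0, the shifts are therefore an upper bound on what an LVEF derivation would recover.

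**5. Sample size re-assessment.** SAP 6.2 divides 54 by the observed proportion with a reason (prop_referral_reason) without naming its source. If the referral CRF is the source, then at p = 0.70 and f = 20% the proportion falls from 0.30 to 50.76/180 = 0.282, and enrolment becomes 54/0.282/0.90, about 213. At f = 40% it is 47.52/180 = 0.264, giving about 227.

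**The case against.** The strongest reply has five parts.

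*The denominator is the ticked criteria, not the yes/no item.* This is correct on the wording, but the tick-boxes sit beneath the *yes* answer, so a *no* normally leaves none ticked. The planned comparison of LVEF of 40% or less with other reasons (SAP 7.9.1.3) suggests that LVEF is one of the boxes. The site must still tick it.

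*Upward bias is not established.* This stands. A reader might infer that a physician who does not refer will also answer *no* to remove the patient. The documents do not support that. SAP 5.1 states: "Referral of patients to SCD risk stratification and management is at the discretion of the physicians". Protocol 9.6 says that non-referral is not a deviation, and the referral CRF has its own field for reasons for not referring (SAP 7.9.5.3), so there is little to hide. Nor do the documents say that the referring physician completes the item: the site enters the data, and the principal investigator or a delegate signs off (Protocol 9.9, 14.2). A misreading of the term referral criteria could affect referred and non-referred subjects alike. A reader might also infer that the distortion is worst at low-awareness sites; Protocol 4.1 mentions low physician awareness in general, but nothing ties recording errors to particular sites.

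*Data controls exist.* Programmed and manual checks, queries and source verification are planned (Protocol 14.1, 14.2). A check of LVEF against the referral CRF is not described, but the CRFs are under separate cover, so its absence cannot be assumed. A data check would also not replace an analysis rule.

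*A bare LVEF override could add error.* This stands. Protocol Table 2 and 9.6.1 set minimum times for the 3-month LVEF that depend on revascularization, whereas the visit window opens at day 40. An early low LVEF in a revascularized subject may not be a wrong *no*.

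*Other tables would show a large gap.* This is partly so. Table 10 counts LVEF of 40% or less by region, but in aggregate; it cannot identify the discordant subjects or their referral status.

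**Conclusion.** The point holds in a limited form. As written, the SAP can leave a subject with a recorded, pre-defined reason for referral out of the primary proportion, and it has no rule reconciling the two forms. The route to a wrong *no* is plausible because the documents disagree on whether LVEF belongs to the referral criteria.

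Direction and size are unknown. The bias is upward if the omitted subjects are mostly non-referred, zero in expectation if errors are equal in the two groups, and downward if they fall mainly on referred subjects. Under the first assumption, error rates of 20% and 40% give shifts of about 5 to 12.5 points across true proportions of 30% to 70%. At the planning value of 70% the shifts stay inside the planned half-width of 12.5 points. They rest on assumed error rates and bound what the fix can recover. The planned 54, 180 and 200 are unaffected.

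**What to change.** In SAP 7.9.1.3:

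1. Define the denominator as a 3-month LVEF of 40% or less on the LVEF CRF that meets the plan's own timing condition (Protocol Table 2 and 9.6.1), **or** any other criterion ticked on the referral CRF.
2. Where the LVEF is missing or mistimed, use the referral CRF answer.
3. State whether subjects exited with LVEF of 50% or more who have another reason are counted in the primary proportion.
4. Tabulate disagreements between the LVEF CRF and the referral CRF by region and referral status. This shows the direction of any bias.
5. Report the CRF-only version as a sensitivity analysis.

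In SAP 6.2, use the same derivation for prop_referral_reason. Reconcile Protocol 9.6 and the Figure 1 footnotes in both documents with SAP 7.9.1.2 on whether LVEF is one of the referral criteria.

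The cost is SAP wording, a little more programming and some discordant cases to query. The analysis uses data already collected. If the forms agree, the estimate does not change.
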